3.0 STUDY DESIGN AND METHODOLOGY

3.1 Study Design

The pivotal evaluation of the AFRS investigational device will incorporate a multi-center, prospective, randomized, and concurrently controlled study design. Up to 30 sites will enroll and treat a minimum of 300 patients and a maximum of 750 patients into the study. In addition, up to 60 training cases (two per clinical site) may be completed by participating investigators, at the discretion of the Sponsor and participating site clinicians.

The investigational group will consist of at least 200 patients who receive the AFRS device. The control group will consist of at least 100 patients who will receive an instrumented posterolateral fusion. This number is based upon the sample size required to provide reasonable assurance of safety and effectiveness using the concurrent control and allowing for 15 percent loss to follow-up. The patients will be allocated to treatment assignment using a 2:1 randomization scheme.

The outcome measures in this study will include the following: the SF-36 questionnaire, the ZCQ, the ODI, a neurological assessment, a symptomatic pain assessment, as measured with the VAS Index, a patient satisfaction questionnaire, and an independent radiological assessment. In addition, outcome measures will be included to support potential reimbursement with healthcare providers. Patients in both treatment groups will be followed for 24 months postoperatively.

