5.2 Randomization Procedure

Patients will be randomly assigned on a two to one (2:1) basis to either the treatment or control group. Randomization will be stratified by clinical center and permuted block randomization will be performed within strata. The block size will be variable and randomly chosen from small multiples of 3. The randomization schedules for the study will be prepared in advance by the study statistician or designee. Investigational sites and the Sponsor will not have access to the randomization schedules.

Treatment assignments will be provided by the statistician for each site completed either by sealed envelopes or an electronic web-based program. If envelopes are used, they will be sealed and sequentially numbered with one envelope per patient. Once distributed to the sites, they will remain sealed until a prospective patient had passed all study criteria. The study coordinator or designee will open the envelope to determine treatment assignment prior to the procedure, allowing sufficient time for insurance authorization. The assignment card will be attached to the Case Report Form. Patient will be blinded to treatment until after the procedure.

Alternatively, a web-based randomization program may be utilized by sites where treatment assignment is made after verification of proper informed consent execution and study eligibility.

Any patient consented, whether randomized or not, will be assigned a patient number. The reason for failure to randomize or failure to treat will be recorded in his/her study records.

If a randomized patient is withdrawn prior to treatment, the next patient will be assigned the next randomly determined treatment as per the study randomization plan until a sufficient number of patients have been treated for each group.

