8.3 Randomization, Sample Size, and Analysis Plan

This study is designed to adaptively determine the proper sample size. Possible sample sizes are 300, 450, 600, and 750 (maximum). Randomization will follow a 2:1 (treatment:control) allocation ratio and be stratified by site, using a blocked randomization scheme with blocks of randomly varying sizes. Further details on the randomization process are provided in **Section 5.2**.

In addition to the planned interim analyses that will determine the sample size, there will be several interim analyses conducted for the purpose of possibly declaring an early win. The first of these will occur when 300 subjects have completed 2 years of follow-up. If the trial does not stop for success at that analysis, a second analysis will occur when 450 have completed 2 years of follow-up. If the trial does not stop for success at that analysis, a final analysis will occur when the entire enrolled cohort has completed 2 years. It is not necessary for the trial to have stopped enrollment in order for the interim “Early Win” analyses to occur. For example, the first Early Win analysis (when 300 have completed 2 years) will occur even if the trial is still enrolling (i.e., the sample size determination algorithm has not determined the final sample size). Of course, if the final sample size is 300, there can be only 1 Win analysis (when the full cohort has reached 2 years); if the final sample size is 450, there can be only 2 Win analyses (when 300 have reached 2 years and when the full cohort has reached 2 years).

The sample size determination analyses and the “Early Win” interim analyses are triggered by different circumstances (number enrolled versus number completing 2 years) and are expected to follow different analysis schedules (i.e., although it is possible, a sample size analysis and an early win analysis are unlikely to occur simultaneously).

Further details on this analysis plan are given below.

Determination of Non-Inferiority and Superiority (“Win” Analyses)

Interim “Win” analyses are scheduled to occur when 300 and 450 subjects have completed 2 years of follow-up. A final analysis will occur when the entire enrolled cohort has completed 2 years of follow-up. At each of these analyses, the probability of non-inferiority $\Pr(H_{\delta=0.15} | \text{data})$ will be calculated, based on all observed data, including predicted 2-year outcomes for those subjects who have not reached 2 years.

[REDACTED]

[REDACTED]

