8.7 Secondary Objectives

General Considerations for Secondary Objectives

While there are many pre-specified secondary objectives, only the first five are designated as objectives for which FDA-approved labeling claims may be sought, and only for the results measured at the 24-month time point. The rest of the secondary objectives have been pre-specified but are intended to be explanatory and supportive in nature, and not the basis of specific labeling claims.

As indicated in “Analysis Methods for Secondary Objectives,” below, flat or diffuse prior distributions have been identified for all secondary objective analyses. For any hypothesis test, a posterior probability greater than 95% for any hypothesis will be considered to constitute evidence in favor of the hypothesis, in the same sense that a frequentist analysis would reject a null hypothesis when $p < 0.05$ and call it “statistically significant.” However, for the subset of secondary objectives on which labeling claims may be sought, the posterior probability threshold for making the claim is somewhat more stringent. See the section entitled “Multiplicity Considerations,” below.

Zurich Claudication Questionnaire (ZCQ) – Physical Function Domain (PF)

The ZCQ PF domain scores for subjects in each treatment group will be summarized at the 3-, 6-, 12-, and 24-month time points. For the 24-month time point, a statistical test will be conducted. The relevant hypothesis is

$$H: \mu_t - \mu_c < \delta$$

where μ_t and μ_c are the average PF scores in the treatment and control groups, respectively, and δ is the margin of non-inferiority.

[REDACTED]

[REDACTED]

Zurich Claudication Questionnaire (ZCQ) – Symptom Severity Domain (SS)

The ZCQ SS domain scores for subjects in each treatment group will be summarized at the 3-, 6-, 12-, and 24-month time points. For the 24-month time point, a statistical test will be conducted. The relevant hypothesis is

$$H: \mu_t - \mu_c < \delta,$$

where μ_t and μ_c are the average SS scores in the treatment and control groups, respectively, and δ is the margin of non-inferiority.

[REDACTED]

[REDACTED]

Back Pain on Visual Analog Scale (VAS)

The back pain VAS scores for subjects in each treatment group will be summarized at the 3-, 6-, 12-, and 24-month time points. For inference, the relevant hypothesis is

$$H: \mu_t - \mu_c < 0,$$

where μ_t and μ_c are the average back pain VAS scores for subjects in the treatment and control groups, respectively. [REDACTED]

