Narcotic Medication Usage

The proportions of subjects in each treatment group who are not on narcotic pain relieving medications and in whom an epidural injection, denervation procedure or other procedure for pain management has not been performed at the index level will be summarized at the 3-, 6-, 12-, and 24-month time points. For the 24-month time point, a statistical test will be conducted. The relevant hypothesis is

$$H: p_t - p_c > 0,$$

where p_t and p_c are the proportions of subjects in the treatment and control groups, respectively, who are not taking narcotic medications and have not had pain management procedures at the index level. [REDACTED]

[REDACTED]

Length of Hospital Stay

The length of hospital stay will be calculated for each subject (with the day of surgery = Day 0) and summarized by treatment group. A statistical test of the difference in length of stay between treatment groups will be conducted. The relevant hypothesis is

$$H: \mu_t - \mu_c < 0$$

where μ_t and μ_c are the average stays in the treatment and control groups, respectively. It is anticipated that the distribution of hospital stays will be somewhat skewed, so the data will be ranked and the statistical method will be the Bayesian version of the Wilcoxon Rank-Sum test, described below. If a subject should die in hospital before being discharged, that subject will be assigned a length of stay that is 1 day greater than the maximum observed length of stay for any patient.

Duration of Procedure

The duration of the procedure will be summarized for the treatment and control groups. Statistical summaries will include means, medians, and standards of deviation, as well as 95% credible intervals for μ_t , μ_c , and $(\mu_t - \mu_c)$. A statistical test will be conducted on the hypothesis

$$H: \mu_t - \mu_c < 0$$

where μ_t and μ_c are the average procedure durations in the treatment and control groups, respectively. The statistical method will be the Bayesian version of a t-test, described below.

Instrumentation Time

The portion of the procedure time that is due to Instrumentation Time will be summarized for the treatment and control groups. Statistical summaries will include means, medians, and standards of deviation, as well as 95% credible intervals for μ_t , μ_c , and $(\mu_t - \mu_c)$. A statistical test will be conducted on the hypothesis

$$H: \mu_t - \mu_c < 0,$$

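### Randomisation is stratified by centre, but the readable text names no centre term for procedure time, instrumentation time, blood loss or hospital stay; if centres differ, these comparisons are conservative

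*Combined protocol and SAP*

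**What the plan says.** Section 5.2 states: "Randomization will be stratified by clinical center and permuted block randomization will be performed within strata". It adds: "The block size will be variable and randomly chosen from small multiples of 3". Section 8.3 repeats the scheme: "Randomization will follow a 2:1 (treatment:control) allocation ratio and be stratified by site". On size, Section 3.1 says: "Up to 30 sites will enroll and treat a minimum of 300 patients and a maximum of 750 patients into the study".

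Section 8.7 tests a directional hypothesis for each of the four endpoints.

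- Procedure duration, instrumentation time and blood loss: "The statistical method will be the Bayesian version of a t-test, described below". For these three, "Statistical summaries will include means, medians, and standards of deviation, as well as 95% credible intervals for" each arm mean and the difference between arms.
- Length of hospital stay: "the data will be ranked and the statistical method will be the Bayesian version of the Wilcoxon Rank-Sum test, described below". No interval is stated.

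The general rule for secondary objectives is that "a posterior probability greater than 95% for any hypothesis will be considered to constitute evidence in favor of the hypothesis", with flat or diffuse priors. Only the first five secondary objectives may support labelling claims. These four are not among them and are described as explanatory and supportive.

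The methods are said to be described below, which points to Section 8.8. That section is in the table of contents but redacted in the body. Section 8.9 tabulates procedure variables and secondary endpoints by site. Its two-factor ANOVA (treatment and site) stands in the paragraph on selected baseline variables. It says that a variable or site found to differ may receive special consideration later.

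**The concern.** Blocking within centre keeps the arms close to 2:1 at every site, so differences between centres largely cancel out of the estimated treatment difference. A two-group t-test or rank-sum test with no centre term does not use this: it counts the between-centre spread as noise. If that spread is real, the interval for the difference is too wide, the 95% posterior threshold acts more strictly than it appears to, and true differences are missed more often.

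Centre differences are plausible here. Sections 5.3 and 5.4 leave immediate postoperative care and discharge to hospital or physician practice, and Section 3.4 leaves graft volume to the investigator. The documents do not say how large the differences are.

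**Working it through.** **Nothing to reproduce.** The readable text gives no SD, effect size, power or interval width for these endpoints. The check therefore compares the same trial analysed with and without centre.

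**Inputs from the documents:** 2:1 allocation; permuted blocks within centre in small multiples of 3 (simulated as 3, 6 and 9); up to 30 sites; 300 patients (the minimum), so 200 against 100; a 95% posterior threshold on a directional hypothesis which, with flat priors, behaves like a one-sided 5% test.

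**Assumptions, not in the documents:** total SD = 1; share of variance between centres ρ from 0 to 0.40; sites of unequal size.

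**Formula.** Unadjusted SE of the difference = √(1/100 + 1/200) = 0.1225 SD. With near-balance inside each centre, the true spread of the estimate is about 0.1225 × √(1 − ρ). The unadjusted SE is therefore too large by a factor of 1/√(1 − ρ):

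- ρ = 0.10: 1/√0.90 = 1.05
- ρ = 0.20: 1/√0.80 = 1.12
- ρ = 0.40: 1/√0.60 = 1.29

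For power, the effect was set to give 80% without adjustment: (1.645 + 0.842) × 0.1225 = 0.305 SD.

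**Simulation.** 2,500 trials per setting, 30 sites. The pooled t-test was compared with a linear model with fixed site effects. The rank-sum test was compared with a site-adjusted rank test (ranks centred within site).

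| ρ | Width, unadjusted / adjusted | Ratio | Unadjusted coverage, no effect / effect | False positives (t), unadjusted / adjusted | Power (t), unadjusted / adjusted | Power (rank), unadjusted / adjusted |
|---|---|---|---|---|---|---|
| 0 | 0.482 / 0.488 | 0.99 | 95.4% / 94.8% | 5.3% / 5.1% | 80.0% / 79.0% | 78.5% / 77.6% |
| 0.10 | 0.480 / 0.463 | 1.04 | 95.1% / 96.5% | 4.9% / 5.4% | 82.1% / 83.8% | 80.6% / 82.2% |
| 0.20 | 0.480 / 0.437 | 1.10 | 96.7% / 97.0% | 4.3% / 5.8% | 83.3% / 87.1% | 81.0% / 84.9% |
| 0.40 | 0.476 / 0.378 | 1.26 | 98.7% / 98.1% | 2.0% / 5.0% | 85.2% / 93.6% | 83.0% / 92.3% |

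Widths are in SD units; for ρ = 0 and 0.10 they are from the runs with an effect. Averaging the two coverage figures gives about 96%, 97% and 98% at ρ = 0.10, 0.20 and 0.40. The power lost is 1.7, 3.8 and 8.4 points for the t-test, and 1.6, 3.9 and 9.3 points for the rank test. The simulated width ratios fall slightly below the formula because small sites end with incomplete blocks. With 20 sites the ratios are much the same: 0.480/0.460 = 1.04, 0.478/0.433 = 1.10 and 0.472/0.375 = 1.26.

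The simulation error is about √(0.95 × 0.05/2500) = 0.4 points on coverage and false positives, and √(0.8 × 0.2/2500) = 0.8 points on a single power figure. At ρ = 0.10 the unadjusted false-positive rate cannot be told apart from 5%.

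**The case against.** The strongest objection is that the specification lies in redacted text. All four entries defer to Section 8.8, so a reader who infers that the plan has no centre adjustment at all goes further than the documents allow. This makes the point conditional but does not remove it. The names given are those of two-group tests, and where Section 8.9 wants site in a model it says so.

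The second objection is that the loss depends on between-centre variance that is nowhere stated. This stands. At ρ = 0 nothing is lost, and at 10% the loss is about 2 points. Nor does unadjusted power drop below its 80% starting value in the t-test simulations. What is lost is precision that the design could have delivered, not a shortfall against a target.

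The third is that Section 8.9 already looks at site. It does, through by-site tables, a site model for the primary outcome, and possible later attention to sites that differ. It does not make site a planned term in these four comparisons.

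Several stronger readings are tempting but unsupported:

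- A reader might infer that all the stated intervals are too wide. None is stated for length of stay, and the cancellation argument covers only the difference, not the separate arm means.
- A reader might infer a risk of false claims. The error is conservative, and these endpoints carry no labelling claim.
- A reader might extend the point to the 24-month scores, whose methods cannot be read, or ask for the number of stenotic levels as a covariate. No such count is listed among the screening data, and the calculation did not test one.

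**Conclusion.** The point holds in conditional form. The readable text pairs centre-stratified randomisation with two-group methods that name no centre term. If Section 8.8 adds none and centres differ, inference on the treatment difference is conservative. For ρ between 0.10 and 0.40 the excess interval width is about 4–26% on three endpoints, and the power lost is about 2–9 points across the four.

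These figures rest on the assumed centre share, normal outcomes, 300 patients, 30 sites and fixed site effects without pooling of small sites. The importance is minor: the endpoints are supportive, no power is claimed for them, and there is neither bias nor type I error inflation.

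**What to change.** Check Section 8.8 first. If it already includes centre for these endpoints, say so in the four entries of Section 8.7 and change nothing else. If it does not:

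- For procedure duration, instrumentation time and blood loss, prespecify a Bayesian linear model with treatment and centre. Centre may be a random intercept, or a fixed effect with centres of fewer than seven patients pooled as in Section 8.9. Report the credible interval for the difference from this model.
- For length of stay, prespecify a centre-stratified rank analysis and keep the existing rule for in-hospital deaths.

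The cost is SAP wording and a slightly larger model. Centre is already recorded, so no new data are needed. If centres turn out not to differ, the price is about 1% in interval width (0.488 against 0.482) and about 1 point of power. Fixing the model in advance also removes a data-driven choice about whether to adjust.

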8.9 Poolability Analyses

To evaluate differences among sites in the study, summary tables by site will be presented and compared for important baseline variables, including demographics and medical history, baseline clinical variables, and procedure variables, as well as for the primary and secondary endpoint variables. Centers with fewer than seven participants will be pooled. Continuous variables will be presented by site in terms of percentiles (e.g., median, 25th and 75th percentile). For categorical parameters, data will be summarized by site using relative frequencies.

Comparisons will be made across sites for selected baseline variables. Continuous data will be compared across sites using a one-way analysis of variance, with a term for site. A two-factor ANOVA with treatment group and site as factors will be used to assess differences among sites and site by treatment interactions. Dichotomous data will be similarly analyzed via logistic regression analysis. If variables are observed to differ by study site, that variable and/or study site may be identified for special consideration in subsequent analyses.

The site effect will be further examined in a multivariable analysis to determine if site is independently associated with outcome. Tests for differences in rates of the primary outcome between treatment groups across sites will be performed using a logistic regression model with terms for sites, treatment assignment, and site-by-treatment interaction. If an association between center and treatment effect is identified, center differences will be further evaluated by assessing the endpoint with and without the center(s) for which the differences are observed, so that the impact of the center(s) can be assessed.

A similar evaluation of poolability will be undertaken for the following subgroups: 1) anatomical stenosis location (lateral, lateral recess or central), 2) number of levels requiring decompression, 3) presence or absence of spondylolisthesis at either the treatment or adjacent level, 4) smoking status during the study..

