5.1 Screening/Pre-Procedure

Patients presenting with stenosis will potentially be eligible for participation in the study. Before being considered for enrollment into this clinical evaluation or receiving any study-specific diagnostic tests and/or questionnaires to further determine eligibility, the Informed Consent Form must be completed and signed by the patient.

Once an Informed Consent Form has been successfully completed, the patient will be evaluated for his or her ability to meet the inclusion and exclusion criteria. Only those individuals who meet all of the inclusion criteria and none of the exclusion criteria are to be enrolled in the study. A list of consented patients excluded from enrollment into this study, or considered patient screen failures will be maintained for each investigation site. The following screening procedures and baseline data are collected for all patients.

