5.1.1 Patient History

Patient demographics and medical history will be completed by the physician or assigned medical personnel. Specific parameters include:

- Age
- Gender
- Height/weight
- Smoking status
- Work status
- Education level
- Duration of pain
- Concurrent health conditions
- Medication use
- Previous surgeries/treatments

- Previous conservative treatment modalities

The patient should demonstrate failure to improve with conservative, non-surgical treatment for a minimum period of six months. Conservative, non-surgical treatment options may include, but is not limited to, medications, NSAIDs, physical therapy, bracing, chiropractic manipulation, modified activities of daily living, epidural injections, facet block injections;

Those patients who are smokers will be advised that they need to stop smoking for a period of 6 weeks after the procedure in order to be eligible for study participation.

Female patients of childbearing potential must have a negative pregnancy test within 14 days prior to treatment and must agree to avoid pregnancy during the course of the study

For those patients that enter the study with a previous surgery, information is collected on the case report form to provide as much detail as possible on the nature of the surgery including type, date, parameters of bone or device removal or other information that may be useful in analyzing the procedure and its affect on the patient.

A comprehensive physical examination will be conducted at baseline and any abnormal findings will be recorded on the CRF. Physical examinations at follow-up visits will be symptom directed only.

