5.4 Patient Discharge

Prior to discharge, patients are examined and evaluated for the presence of any adverse events that may have occurred between the operative procedure and discharge. Patient discharge from the hospital will be accomplished according to standard hospital/physician practice. Patients are eligible for discharge based on the following criteria:

- Patient is able to ambulate
- Surgical wound is confirmed as intact, with no signs of infection
- Patient bodily functions are active

Patient discharge from the hospital will be accomplished according to standard hospital/physician practice. Prior to discharge the patient may be fitted with a brace at the investigator's discretion. The brace will be removed at the 6-week follow up visit or earlier based on the Investigator's discretion.

The following data is collected at discharge:

- Static AP radiographs
- Static lateral radiographs
- Duration of hospital-stay and hospital discharge date
- Pain and antibiotic medication use
- Adverse events

Bone growth stimulators are not to be used during the course of this study. This study does not specify the use of prophylactic antibiotic medications. Medications may be administered at the discretion of the physician. After discharge, patients are not to receive

epidural spinal injections or nerve blocks for pain relief within six weeks of a scheduled study visit, as this will confound the collection of pain and function data.

Additionally, patients receiving post-procedure denervation procedures, at the index level, within the 24 month follow up evaluation period will be considered study failures.

Patients will be instructed to avoid smoking and use of systemic (IV, PO or transdermal patch) steroidal therapy during the first six weeks of post procedure bone healing and informed that this may affect their recovery. For the purposes of this study, use of inhalers containing steroids are not considered systemic use.

All patients will receive postoperative rehabilitation therapy as directed by the investigator with the objective of improving strength, flexibility and mechanics. This therapy will not be standardized as the program is required to be specific for each patient's need. Bending and lifting should be avoided during the first 6 week period postoperative period.

The discharge instructions contained in **Appendix 4** (or site equivalent) will be explained and provided to the patient upon hospital discharge.

[REDACTED]

[REDACTED]

[REDACTED]

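### The smoking subgroup in Section 8.9 is defined after randomisation, so its treatment interaction may be confounded; baseline smoking, already collected, is the cleaner factor

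*Combined protocol and SAP*

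**What the plan says.** Section 8.9 sets out how site differences will be examined. For the primary outcome it specifies a "logistic regression model with terms for sites, treatment assignment, and site-by-treatment interaction". If the treatment effect appears to vary by centre, the endpoint is assessed with and without the centres concerned. The section then says: "A similar evaluation of poolability will be undertaken for the following subgroups". The list has four entries. The first three (stenosis location, number of levels needing decompression, spondylolisthesis) read as features of the presenting condition. The fourth is "smoking status during the study".

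Four other places bear on that definition:

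- Section 5.1 introduces the screening items: "The following screening procedures and baseline data are collected for all patients". Section 5.1.1 lists "Smoking status" among them.
- Section 5.1.1 also states: "Those patients who are smokers will be advised that they need to stop smoking for a period of 6 weeks after the procedure".
- Section 5.4 repeats the advice at discharge: "Patients will be instructed to avoid smoking", with reference to the first six weeks of bone healing.
- Section 5.2 states: "Patient will be blinded to treatment until after the procedure".

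The readable text gives no time window for on-study smoking, no rule for patients who quit or relapse, and no additional subgroup based on baseline smoking.

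**The concern.** An interaction test asks whether the treatment effect differs between types of patient. Randomisation supports that question when the types are fixed at baseline, because the arms are then comparable within each type. On-study smoking is not fixed at baseline. It can respond to the arm a patient turns out to be in, to recovery, and to the advice to stop. If it responds differently in the two arms, on-study smokers on the facet device and on-study smokers with fusion are no longer the same kind of patient, and neither are the two non-smoking groups.

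Success is judged at 24 months, so smoking over that period may also be partly a result of how the patient is doing. The split could then show an interaction where there is none, or hide a real one. What is at stake is the reading of one poolability table and any statement in the report that the device works differently in smokers.

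**Working it through.** The plan gives no smoking prevalence, quit rate or subgroup size, so there is no figure to reproduce. The check has two parts.

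**1. Order of events, from the documents.** Smoking status is recorded at screening (5.1.1). Randomisation follows the baseline procedures and precedes surgery (4.0). The patient's blinding lasts only until after the procedure (5.2). Smokers are asked to stop for six weeks after it (5.1.1, 5.4). The variable in 8.9 covers the period after all of these. It is therefore a post-randomisation variable that the protocol expects to change, while a pre-randomisation version exists.

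**2. Could this produce a false interaction? Illustration under assumptions; none of these rates come from the documents.** Suppose treatment has no effect in any patient and each patient type has a fixed success rate:

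- Baseline non-smokers: 65%.
- Smokers who continue in either arm: 40%.
- Smokers who would quit in either arm: 60%; they are 20% of baseline smokers.
- Smokers who would quit only in the control arm (the arm-dependent type): 60%; they are a fraction d of baseline smokers.

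Success in each on-study group is the average over the types in it, weighted by their shares. The apparent interaction is (treatment minus control in on-study smokers) minus (treatment minus control in on-study non-smokers).

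Worked case with 25% baseline smokers and d = 20%. Shares of all patients are 0.75 non-smokers, 0.15 continuers, 0.05 quitters in either arm and 0.05 arm-dependent.

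- On-study smokers, treatment: (0.15 × 0.40 + 0.05 × 0.60) / 0.20 = 45.0%. Control: 40.0%. Difference +5.0 points.
- On-study non-smokers, treatment: (0.75 × 0.65 + 0.05 × 0.60) / 0.80 = 64.7%. Control: (0.75 × 0.65 + 0.10 × 0.60) / 0.85 = 64.4%. Difference +0.3 points.
- Apparent interaction: about 4.7 points. Truth: 0.
- Split by baseline smoking instead: smokers 0.6 × 40% + 0.4 × 60% = 48% in both arms, non-smokers 65% in both arms. Interaction 0.

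Range, with 15%, 25% or 35% baseline smokers and 55% or 60% success in the arm-dependent type:

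| d (quit in one arm only) | Apparent interaction, points |
|---|---|
| 0% | 0 |
| 10% | 1.4 to 2.4 |
| 20% | 2.9 to 4.8 |
| 30% | 4.4 to 7.3 |

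On the log odds ratio scale, 10% to 30% gives 0.06 to 0.30.

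**Outcome-driven smoking, among baseline smokers only.** Assume 55% success in both arms, 80% of failures smoking in both arms, and 70% (treatment) v 50% (control) of successes smoking.

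- On-study smokers: 0.385 / 0.745 = 51.7% v 0.275 / 0.635 = 43.3%, a difference of +8.4 points.
- On-study non-smokers: 0.165 / 0.255 = 64.7% v 0.275 / 0.365 = 75.3%, a difference of -10.6 points.

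The true difference is 0. In the full trial the second figure would be diluted by baseline non-smokers. If smoking is set to 60% in every arm and outcome group, both differences are 0.

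**The case against.** The strongest reply is that bias needs on-study smoking to depend on arm, or on arm and outcome jointly, and nothing in the documents shows that it does. The advice in 5.1.1 and 5.4 is the same for both arms. This stands. A reader might infer that any difference between on-study smokers and non-smokers can never be a treatment interaction; the documents support only that it may be confounded.

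The illustration also has limits. It rests on assumed rates and treats the gap between quitters and continuers as selection. If the gap were caused by quitting itself, and quitters were otherwise like continuers, the smoker group would hold the same kind of patient in both arms and show no false difference.

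A reader might also infer from Appendix 1, which has no smoking row at follow-up, that smoking is not collected after baseline. That does not follow. Appendix 1 has no smoking row at screening either, where 5.1.1 does collect it, and it omits the return-to-work and rehabilitation questionnaire that 5.6.8 collects at every follow-up visit. Case report forms or redacted text may define on-study smoking, although no definition would make it a baseline variable.

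Nor does 8.9 attach a decision to the subgroup result. Its provision for special consideration is written for variables that differ by site, is optional, and reaches smoking only by analogy.

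Finally, exposure during bone healing is a fair question, and baseline status may misstate it. That is a reason to keep an on-study analysis, but not as the interaction factor.

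**Conclusion.** The point holds as a modest one. Section 8.9 puts a post-randomisation variable into an interaction evaluation although a baseline version is already collected, and the resulting interaction may be confounded by selection after randomisation. The direction and size cannot be derived from the documents. Under the assumptions shown, the false interaction runs from 0, when on-study smoking does not depend on arm, to 7.3 points, when 30% of baseline smokers quit in one arm only. The larger contrast in the outcome-driven example shows a mechanism and is not an estimate.

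A reader might infer that the trial's main conclusion is at risk. It is not: Section 8.3 bases the primary decision on the posterior probability of non-inferiority, and this supportive analysis does not enter it.

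**What to change.** In Section 8.9, define subgroup 4 as smoking status at baseline, as recorded under 5.1.1, and use that as the factor in the treatment-by-smoking interaction.

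Keep on-study smoking as a separate exploratory analysis, including outcome by exposure if the sponsor wants it. State its time window, its data source and the rule for patients who quit or relapse, and label it as not supporting an interaction conclusion.

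The cost is a few words in 8.9 plus one definition. The baseline subgroup needs no new data. Keeping the exploratory analysis preserves the look at exposure during healing that would be lost if on-study smoking were removed altogether.
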